6.1 DETERMINATION OF SAMPLE SIZE

This study is intended to obtain preliminary safety, PK, PD, and activity information. The sample sizes do not reflect any explicit power and type I error considerations.

The range of mean Ki67 expression changes are from 66% (Opportune) to 76% (IMPACT) for 2-week treatment (see Section 3.3.4.1). The planned enrollment for this study is approximately 75 patients. *At least 15 patients per cohort will provide a more robust safety profile as well as sample size for preliminary assessment of activity based on Ki67 expression. In Table 4, two-sided 80% CIs for Ki67 expression changes are listed, based on different assumed observed changes. The CIs show clear shift pattern at the sample size of 15 patients. To better evaluate the Ki67 expression change at 30 mg, the sample size is increased to 45. The 80% CIs show clear separation at this patient sample size.*

Table 4 Two-Sided 80% Confidence Intervals for Ki67 Expression Change

Sample size	Assumed Observed Change			
	60%	70%	80%	90%
15	(53.9%, 66.8%)	(62.9%, 77.9%)	(71.9%, 89.0%)	(80.9%, 100%)
20	(54.7%, 65.8%)	63.8%, 76.8%)	(72.9%, 87.8%)	(82.0%, 98.7%)
45	(56.4%, 63.8%)	(65.8%, 74.5%)	(75.2%, 85.1%)	(84.6%, 95.7%)

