3.3.4 Rationale for Biomarker Assessments

PD biomarkers will be measured in tissue to determine whether clinically achievable exposures are sufficient for producing the desired effect on the intended molecular target. The evaluation of dose-PD and dose-activity relationships across a range of GDC-9545 doses will enable dose selection.

Breast cancer is a heterogeneous disease (Cancer Genome Atlas Network 2012). Therefore, all patients may not be equally likely to benefit from treatment with GDC-9545. Predictive biomarker samples will be assessed in an effort to identify those patients who are most likely to respond to GDC-9545. PD biomarkers will be assessed to demonstrate evidence of biologic activity of GDC-9545 in patients, to support selection of a recommended dose and dose regimen, and to inform potential revisions to the PK sample collection schedule.

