3.3.4.1 Ki67

Ki67 is a well-established proliferation biomarker with prognostic value in ER-positive breast cancer (Anderson et al. 2011). Efficacy of endocrine therapy relies on induction of cell-cycle arrest, and during neoadjuvant treatment, Ki67 levels reflect the ability of endocrine agents to suppress proliferation (Dowsett et al. 2005b; Ellis et al. 2011). There are numerous examples of endocrine agents used in small, short-term neoadjuvant studies whose Ki67 results parallel disease-free recurrence outcomes from large adjuvant studies or PFS in metastatic studies (Guerrero-Zotano and Arteaga 2017).

In the IMPACT trial, short-term changes of Ki67 during the neoadjuvant period of treatment of primary breast cancer with anastrozole or tamoxifen alone or in combination correlated with recurrence-free survival. In this study, Ki67 was assessed at baseline, on Day 15, and at surgery after 12 weeks of treatment (Dowsett et al. 2005a, 2005b). For each treatment arm, the reduction in geometric mean Ki67 levels was significantly higher for anastrozole (76%) than for tamoxifen at both timepoints ($p=0.004$, $p=0.001$, respectively), but no differences were found between tamoxifen (59%) and the combination of anastrozole and tamoxifen (64%). These results mirrored the statistically significant ($p=0.004$) recurrence-free survival outcome difference between anastrozole and tamoxifen (4.3% at 10 years) in the much larger adjuvant ATAC trial ($n=9366$) without the requirement of a long follow-up. In addition, after a median follow-up of 68 months, anastrozole significantly prolonged disease-free survival (575 events with anastrozole vs. 651 with tamoxifen; HR=0.87; 95% CI: 0.78, 0.97; $p=0.01$) and time-to-recurrence (402 vs. 498; HR=0.79; CI: 0.70, 0.90; $p=0.0005$), and significantly reduced distant metastases (324 vs. 375; HR=0.86; CI: 0.74, 0.99; $p=0.04$) and contralateral breast cancers (35 vs. 59; 42% reduction, CI: 12%, 62%; $p=0.01$) (Baum et al. 2002; Howell et al. 2005; Forbes et al. 2008)

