6.6 ACTIVITY ANALYSES

The activity analysis population will consist of all patients who completed study treatment and who have tumor biopsy specimens available at baseline and at surgery for assessment of activity.

The activity is defined as change from baseline in tumor cell proliferation measured by Ki67 expression between pre- and post-treatment samples. The activity will be summarized by dose level.

On the assumption of a log normal distribution, Ki67 values will be log transformed before analysis. $\log(\text{Ki67}_{\text{post}})$ and $\log(\text{Ki67}_{\text{pre}})$ will be used to denote the mean of the logs of the post-treatment and pre-treatment values, respectively. A value of 0.1 will be added to every untransformed Ki67 value to avoid the mathematical anomaly that arises because the log of zero is minus infinity. The result of mean log changes and CI can be calculated and displayed on their original scale by back transformation.

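### Table 4's 80% intervals are built around the percent Ki67 reduction, not the log post/pre change that Section 6.6 analyses, so precision runs the wrong way across the table; the SD is unstated

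*Combined protocol and SAP*

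**What the plan says.** Section 6.1 states that "The sample sizes do not reflect any explicit power and type I error considerations", and then rests the cohort sizes on precision. It cites benchmark two-week Ki67 changes of 66% to 76%. "In Table 4, two-sided 80% CIs for Ki67 expression changes are listed, based on different assumed observed changes"; the columns are 60%, 70%, 80% and 90%, and the rows are n = 15, 20 and 45. The text reads a clear shift pattern into the n=15 row. It goes on: "To better evaluate the Ki67 expression change at 30 mg, the sample size is increased to 45", and "The 80% CIs show clear separation at this patient sample size". Neither Section 6.1, Section 6.6 nor the synopsis states the SD behind the table or the formula used.

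Section 6.6 adds 0.1 to each Ki67 value, takes logs on a log-normal assumption and works with the mean log change from pre- to post-treatment. It adds: "The result of mean log changes and CI can be calculated and displayed on their original scale by back transformation". No other confidence interval for Ki67 is described.

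On purpose, Section 3.3.4 says: "The evaluation of dose-PD and dose-activity relationships across a range of GDC-9545 doses will enable dose selection".

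**The concern.** A back-transformed mean log change estimates the geometric mean post/pre ratio, and the reduction is one minus that ratio. An interval built this way is tight when suppression is deep, because little Ki67 remains, and its upper limit stays below 100%. Table 4 shows the reverse: its intervals widen as suppression deepens, and one limit sits at exactly 100%. That suggests the log-normal interval was placed on the percent reduction itself.

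Table 4 is the only quantitative support for 15 patients per cohort and for raising the 30 mg cohort to 45. If its scale is not that of the analysis, readers are misled about where Ki67 precision is good or poor, in a study meant to inform dose selection.

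**Working it through.** **Inputs.** Two-sided 80% level, columns, rows and printed limits: Section 6.1, Table 4. Planned scale: Section 6.6. Normal quantile z(0.90) = 1.2816; t(0.90) = 1.345 on 14 df and 1.301 on 44 df. SD: not in the documents, so fitted in step 1 and treated as an assumption afterwards.

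**1. Reproducing Table 4.** Let R be the percent reduction and take limits R × exp(±1.2816 × s/√n). The rounded limits imply s between 0.3222 and 0.3239 (n=15), 0.3227 and 0.3238 (n=20), and 0.3226 and 0.3242 (n=45). Any single s from 0.3230 to 0.3235 reproduces all 24 limits. With s = 0.323:

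- n=15: factor 1.1128. 60/1.1128 = 53.9 and 60 × 1.1128 = 66.8, as printed. 90 × 1.1128 = 100.15, printed as 100%.
- n=45: factor 1.0637. 80/1.0637 = 75.2 and 80 × 1.0637 = 85.1, as printed.

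With t quantiles the three implied SD ranges do not overlap (0.307–0.309, 0.312–0.313, 0.318–0.319), so the table used the normal quantile. A symmetric interval fails (−6.1/+6.8 at 60%, n=15). So does a log interval on 1−R: its log half-widths there are unequal, 0.142 and 0.186.

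**2. Could the columns be post/pre ratios?** Then the formula would match Section 6.6. But the text sets the columns against benchmarks of 66% to 76%, and Section 3.3.4.1 gives the upper benchmark as a reduction: "the reduction in geometric mean Ki67 levels was significantly higher for anastrozole (76%) than for tamoxifen at both timepoints". A cap at 100% also belongs to a reduction, not to a ratio.

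**3. The planned interval.** With tau the SD of the change in log(Ki67+0.1), the limits are 100 × [1 − (1−R) × exp(±t × tau/√n)], R now a fraction. The width is proportional to 1−R, so from 60% to 90% it falls by 0.40/0.10 = 4 for any tau common to the columns.

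| | 60% | 70% | 80% | 90% |
|---|---|---|---|---|
| Printed width, n=15 | 12.9 | 15.0 | 17.1 | 19.1 |
| Printed width, n=45 | 7.4 | 8.7 | 9.9 | 11.1 |
| tau needed to match, n=15 | 0.46 | 0.71 | 1.20 | 2.45 |
| tau needed to match, n=45 | 0.48 | 0.75 | 1.26 | 2.73 |

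No single tau reproduces the table. With the normal quantile the n=15 matches are 0.49, 0.75, 1.26 and 2.57, so the choice of quantile does not matter to the conclusion.

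**4. Size, conditional on tau.**

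- Benchmark range: the table's formula gives about the right width if tau is about 0.6 (at 66%) to 1.0 (at 76%). At 70%, n=45, tau = 0.75 gives (65.3, 74.1) against the printed (65.8, 74.5).
- At 60%, n=15, tau = 1.0 gives (43.4, 71.7) against (53.9, 66.8).
- At 90%, n=15, tau = 1.0 gives (85.8, 92.9) against (80.9, 100).

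**5. The separation sentence.** In the printed n=45 row, 60/70 separate (63.8 below 65.8) and 70/80 separate (74.5 below 75.2), but 80/90 overlap (85.1 above 84.6). Only the 30 mg cohort has 45 patients; the other two share about 75 − 45 = 30, or about 15 each. At 45 for the lower value against 15 for the higher, no adjacent printed pair separates: 63.8/62.9, 74.5/71.9, 85.1/80.9.

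On the planned scale two intervals separate when tau < ln[(1−R1)/(1−R2)] / (t1/√n1 + t2/√n2), where t/√n is 0.194 at n=45 and 0.347 at n=15:

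| Pair | ln ratio | 45 v 45 (÷ 0.388) | 45 v 15 (÷ 0.541) |
|---|---|---|---|
| 60/70 | 0.288 | tau < 0.74 | tau < 0.53 |
| 70/80 | 0.405 | tau < 1.05 | tau < 0.75 |
| 80/90 | 0.693 | tau < 1.79 | tau < 1.28 |

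On the printed table separation gets harder as suppression deepens; on the planned scale it gets easier.

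**The case against.** The strongest reply is that the table is descriptive planning material. The plan disclaims power and type I error, Table 4 feeds no test or decision rule, and no reported estimate will change. That is true and limits the severity. It does not make the table right, and the table is the only numerical basis offered for the cohort sizes.

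The fourfold narrowing needs tau to be the same at every level of suppression. Ki67 values near zero can inflate spread on the log scale, so this is not guaranteed. The qualification stands. However, Table 4 itself uses one SD for every column, and matching it would need tau to rise more than fivefold between 60% and 90%, which nothing in the documents suggests.

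Because tau is unknown, the table could be conservative: below about 0.46 the planned widths are narrower than printed in every column. This also stands, and any replacement should include a low value.

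On separation, two of the three adjacent pairs in the n=45 row do separate, the third overlaps by only 0.5 point, and the benchmarks lie within the 60% to 80% columns. The plan also specifies no between-cohort comparison, and the increase is described as improving the estimate at 30 mg. So 45 against 15 is not a criterion the plan set itself; it matters only if separation is meant to distinguish the study's actual cohorts, which the text leaves open.

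**Conclusion.** The concern holds. Table 4 describes intervals on a scale the study will not use, with an SD it does not state. Across its columns the printed widths grow by about half (19.1/12.9 = 1.48 at n=15; 11.1/7.4 = 1.50 at n=45) where the planned widths fall to a quarter, given a common tau. The numerical error cannot be fixed without tau. The table is about right within the 66% to 76% benchmarks if tau is about 0.6 to 1.0, too narrow at 60% if tau exceeds about 0.5, and too wide at 90% for any tau below about 2.4. The separation statement is wrong as printed for 80% against 90%, whatever tau is. This should be corrected, but it is a planning-table error and gives no reason to change the cohort sizes or Section 6.6.

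**What to change.** Recompute Table 4 as 100 × [1 − (1−R) × exp(±t(0.90, n−1) × tau/√n)], with tau the SD of the change in log(Ki67+0.1). State tau and its source, use one quantile convention throughout (the normal quantile would serve if stated), and show a small range. For n=45, with illustrative tau values that are assumptions, not taken from the documents:

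| tau | 60% | 70% | 80% | 90% |
|---|---|---|---|---|
| 0.5 | (55.9, 63.7) | (66.9, 72.8) | (78.0, 81.8) | (89.0, 90.9) |
| 0.75 | (53.7, 65.4) | (65.3, 74.1) | (76.9, 82.7) | (88.4, 91.4) |
| 1.0 | (51.4, 67.1) | (63.6, 75.3) | (75.7, 83.5) | (87.9, 91.8) |
| 1.25 | (49.0, 68.6) | (61.8, 76.5) | (74.5, 84.3) | (87.3, 92.2) |

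Reword the shift and separation sentences to match the new figures, and say whether separation refers to two cohorts of 45 or to the actual 45 against about 15.

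The cost is one recalculated table and two sentences, with no extra patients or procedures. The stated precision will look worse at 60% if tau exceeds about 0.5 and at 70% if it exceeds about 0.75, and better at 90% for any tau below about 2.4.

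### Section 6.1 claims clear separation of the 80% CIs at n=45, but in Table 4 the n=45 intervals for 80% and 90% overlap by 0.5 points

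*Combined protocol and SAP*

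**What the plan says.** Section 6.1 (Determination of Sample Size) introduces Table 4, in which "two-sided 80% CIs for Ki67 expression changes are listed, based on different assumed observed changes", for assumed changes of 60%, 70%, 80% and 90% and sample sizes of 15, 20 and 45. For the smallest size the text says "The CIs show clear shift pattern at the sample size of 15 patients". It continues "To better evaluate the Ki67 expression change at 30 mg, the sample size is increased to 45", and then "The 80% CIs show clear separation at this patient sample size". That last sentence names no particular columns. The same section quotes a benchmark range of 66% to 76% for two weeks of treatment and states: "The sample sizes do not reflect any explicit power and type I error considerations".

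Section 6.6 (Activity Analyses) sets the scale of the planned analysis: "On the assumption of a log normal distribution, Ki67 values will be log transformed before analysis", and "The result of mean log changes and CI can be calculated and displayed on their original scale by back transformation".

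**The concern.** Separation of intervals is a yes-or-no property that can be read off the printed row, and the claim of separation at n=45 carries no qualification. It is also the only thing the text says n=45 achieves beyond n=15. If one of the three adjacent pairs overlaps, the sentence claims a precision that the table does not show. A reader could conclude that observed changes 10 points apart are always told apart with 45 patients. What is at stake is how the precision of the 30 mg cohort is read. No test, stopping rule or dose-selection rule in the document depends on the sentence.

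**Working it through.** **Inputs.** The printed limits of Table 4 (Section 6.1); the two-sided 80% level, giving z = 1.2816; and n = 15, 20 and 45. The documents state no SD, so it has to be recovered from the table.

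**Step 1: reproduce the table.** With m the assumed change, the form

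limits = m × exp(±1.2816 × SD / √n), upper limit capped at 100%

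reproduces all 24 printed limits to one decimal with a single SD between 0.3228 and 0.3237, taken on the log of the percent change. The cap acts in one cell only, the upper limit for 90% at n=15, which is about 100.15 uncapped. A t quantile does not fit all three rows with one SD. At SD = 0.3235 and n = 45 the unrounded limits are 75.21 to 85.10 for the 80% change and 84.61 to 95.74 for the 90% change. The table is therefore internally sound.

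**Step 2: gaps between printed intervals.** Gap = lower limit for the higher change − upper limit for the lower change. A negative gap is an overlap.

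| Pair | n=15 | n=45 |
|---|---|---|
| 60/70 | 62.9 − 66.8 = −3.9 | 65.8 − 63.8 = +2.0 |
| 70/80 | 71.9 − 77.9 = −6.0 | 75.2 − 74.5 = +0.7 |
| 80/90 | 80.9 − 89.0 = −8.1 | 84.6 − 85.1 = **−0.5** |
| 60/80 | 71.9 − 66.8 = +5.1 | 75.2 − 63.8 = +11.4 |
| 70/90 | 80.9 − 77.9 = +3.0 | 84.6 − 74.5 = +10.1 |
| 60/90 | 80.9 − 66.8 = +14.1 | 84.6 − 63.8 = +20.8 |

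**Step 3: rounding.** The most favourable unrounded values consistent with the printed cells are 85.05 and 84.65. The overlap is then 85.05 − 84.65 = 0.40, so rounding does not explain it. This step and step 2 need no SD.

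**Step 4: which pairs the sentence can mean.** All non-adjacent pairs already separate at n=15, where the text claims only a shift. Separation as something gained at n=45 must therefore refer to adjacent columns.

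**Step 5: where adjacent pairs separate under Table 4's method.** For changes a < b, the smallest n is (2 × 1.2816 × SD / ln(b/a))². At SD = 0.323 this gives 28.8, 38.4 and 49.4, that is n = 29 (60/70), 39 (70/80) and 50 (80/90). So 45 is enough for two of the three pairs. These numbers explain the pattern in the table; they are not a proposal to change the sample size.

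**Step 6: what n=45 does deliver.** Printed widths from n=15 to n=45:

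- 60%: 12.9 to 7.4 (43% narrower)
- 70%: 15.0 to 8.7 (42%)
- 80%: 17.1 to 9.9 (42%)
- 90%: 19.1 to 11.1 (42%)

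This agrees with 1 − √(15/45) = 42.3%. On the Section 6.6 scale after back-transformation the narrowing is 42% to 44% for assumed SDs of 0.5 to 1.5 (the documents give none), so the statement does not hinge on Table 4's scale.

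**Step 7: the pair pattern does hinge on the scale.** Section 6.6 works with log post-treatment against log pre-treatment Ki67. Ignoring the added 0.1, the distances between adjacent changes are ln(40/30) = 0.29, ln(30/20) = 0.41 and ln(20/10) = 0.69. Two n=45 intervals separate when SD < distance × √45 / (2 × 1.2816), that is below 0.75 (60/70), 1.06 (70/80) and 1.81 (80/90). There 80/90 is the easiest pair to separate, the reverse of Table 4.

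**The case against.** The case for leaving the sentence alone is about weight. Five of the six n=45 pairs separate, and the sixth fails by half a point. The 60%, 70% and 80% columns, which bracket the 66% to 76% benchmark, all separate. Against n=15, where every adjacent pair overlaps by 3.9 to 8.1 points, the contrast drawn is largely right. The stated purpose of the increase is better evaluation at 30 mg, and narrower intervals serve it whether or not 80/90 overlaps; part of the amendment's rationale is also redacted. Overlap of two 80% CIs is not a test of difference. Moreover, only the 30 mg cohort has 45 patients, so two n=45 intervals never describe two arms of this trial.

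Most of this stands and is why the point is minor. It does not rescue the wording. The sentence is not confined to the benchmark columns, and the 90% column is part of the table it describes. The text does not say which intervals it compares, so step 4 is an inference, but a reading limited to non-adjacent pairs would make n=45 add nothing that n=15 lacked. The fact that only one cohort has 45 patients does not help the claim either: setting printed n=45 limits against n=15 limits 10 points away, every pair overlaps, by 0.9 to 4.4 points. It is fair to say that the undocumented SD and the scale difference from Section 6.6 are separate matters. They are not needed to show the overlap.

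**Conclusion.** The concern holds. At n=45 the tabulated intervals for 80% and 90% overlap by 0.5 points, and by at least 0.4 under the most favourable rounding, so the unqualified statement of clear separation is wrong for one of three adjacent pairs. This rests on the printed limits alone. The SD of about 0.323 and the sizes 29, 39 and 50 are inferred from the table and serve only as explanation. The Section 6.6 thresholds are illustrative, since they ignore the 0.1 offset and no SD is documented for that scale. Severity is minor: the misstatement affects how the precision is described and gives no ground for criticising the tabulated limits, the sample size or the planned analysis.

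**What to change.** Replace the separation sentence in Section 6.1 with, for example: *At n=45 the 80% CI for the 30 mg cohort is about 42% narrower than at n=15; as tabulated, intervals for assumed changes 10 points apart do not all separate (80% and 90% overlap).*

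A one-line note under Table 4 giving the SD and the scale used would help the reader but is secondary. The pair-by-pair pattern in the table should not be presented as a property of the Section 6.6 analysis, where the order reverses.

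The cost is one or two sentences and, if adopted, the table note. The tabulated limits, the cohort size and the analysis stay as they are, and no extra patients are needed. The only loss is that the stated precision reads slightly less favourably.

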6.2 SUMMARIES OF CONDUCT OF STUDY

Summaries of study conduct will include all enrolled patients in the study. The number of patients who enroll, discontinue, or complete the study will be summarized. Reasons for discontinuations and premature study withdrawal will be listed and summarized. Enrollment and major protocol deviations will be listed and evaluated for their potential effects on the interpretation of study results.

6.3 SUMMARIES OF DEMOGRAPHIC AND BASELINE CHARACTERISTICS

Demographic and baseline characteristics (including, but not limited, to age, race/ethnicity, weight, type of malignancy, duration of malignancy, and baseline ECOG Performance Status) will be summarized using means, standard deviations, medians, and ranges for continuous variables and proportions for categorical variables, as appropriate. Summaries will be presented overall and by dose level.

6.4 SAFETY ANALYSES

For safety analyses, the analysis population will include all enrolled patients who receive at least one dose of study medication.

Study treatment discontinuation and reasons for patient discontinuations from the study will be described and summarized. Study drug administration data will be listed and any dose modifications will be flagged.

Safety will be assessed through summaries of adverse events, changes in laboratory test results (including ECGs), changes in vital signs, and GDC-9545 exposure. All adverse events occurring on or after treatment on Day 1 will be summarized by mapped term, appropriate thesaurus levels, and NCI CTCAE v5.0 toxicity grade. Relevant laboratory and vital sign (pulse rate, blood pressure, and temperature) data will be displayed by time, with NCI CTCAE v5.0 Grade 3 and 4 values identified, where appropriate. Additionally, all laboratory data will be summarized by NCI CTCAE v5.0.

Safety data will be accumulated up to the end of the patient's follow-up period.

6.5 PHARMACOKINETIC ANALYSES

The sparse PK concentration data at the steady state will be summarized by dose level and compared with the historical PK profiles from the Phase I study.

Additional PK analyses may be conducted as appropriate.

6.6 ACTIVITY ANALYSES

The activity analysis population will consist of all patients who completed study treatment and who have tumor biopsy specimens available at baseline and at surgery for assessment of activity.

The activity is defined as change from baseline in tumor cell proliferation measured by Ki67 expression between pre- and post-treatment samples. The activity will be summarized by dose level.

On the assumption of a log normal distribution, Ki67 values will be log transformed before analysis. $\log(\text{Ki67}_{\text{post}})$ and $\log(\text{Ki67}_{\text{pre}})$ will be used to denote the mean of the logs of the post-treatment and pre-treatment values, respectively. A value of 0.1 will be added to every untransformed Ki67 value to avoid the mathematical anomaly that arises because the log of zero is minus infinity. The result of mean log changes and CI can be calculated and displayed on their original scale by back transformation.

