Detailed studies in the neoadjuvant setting in prospective randomized clinical trials have demonstrated the utility and validity of changes in Ki67 as a predictor of benefit from of endocrine therapy treatment and of long-term outcome (Dowsett et al. 2005a; Dowsett et al. 2005b; Polychronis et al. 2005; Dowsett et al. 2006; Dowsett et al. 2007; Smith et al. 2007; Ellis et al. 2008; Baselga et al. 2009; Jones et al. 2009) (see Section 3.3.4.1 for additional details).

Although Ki67 measurements in preoperative trials cannot replace the need for adjuvant trials with clinical endpoints, when used along with additional PD data and Phase I dose escalation/expansion safety and efficacy data, they can be highly instructive in selecting the optimal dose for Phase III studies and defining the most appropriate patient populations.

As of November 2018, GDC-9545 has been well-tolerated and shown evidence of activity including in those patients with *ESR1* mutations (see Section 1.2.2). At all doses tested, patients with [¹⁸F]-fluoroestradiol positron emission tomography imaging have shown near-complete or complete responses. In addition, there is early indication of ER-pathway reduction by PD markers in the few on-treatment biopsies obtained from the Phase I study.

Overall, there is strong rationale to run a window of opportunity study to select the optimal dose of GDC-9545. In addition, GDC-9545 has a tolerable safety profile that poses minimal risk for patients during treatment and for surgery.

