3.3.2 Rationale for GDC-9545 Dose and Schedule

GDC-9545 is a potent, orally bioavailable, small-molecule therapeutic agent that is being developed for the treatment of patients with ER-positive breast cancer. Nonclinical anti-tumor activity has been seen in a number of single-agent and combination therapy studies. In addition, early clinical anti-tumor activity has been seen in ER-positive breast cancer. GDC-9545 has demonstrated an acceptable toxicity profile in more than 20 metastatic ER-positive breast cancer patients treated to date. The dose and schedule of GDC-9545 will be orally once daily continuously for 14 days (± 2) and the day of surgery (if allowed). GDC-9545 will be administered at 10, 30, and 100 mg.

The doses selected for the Phase I GO40987 study are 10, 30, and 100 mg (rounded from 90 mg to reduce pill burden on patients). These three doses mirror doses studied in the ongoing Phase Ia/b dose-escalation/expansion GO39932 study and that have already cleared the DLT window in the latter study. The traditional safety and efficacy endpoints are being studied in the Phase Ia/b GO39932 study, while the endpoints for the GO40987 study are biomarkers aimed at defining dose-PD and dose-activity relationships to help guide selection of the recommended Phase II dose.

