4.2 METHOD OF TREATMENT ASSIGNMENT

Treatment assignment will be conducted using an interactive voice or web-based response system (IxRS). After written informed consent has been obtained, all patients will receive a screening number, which will be assigned by the IxRS. Following completion of the screening period and after all patient eligibility requirements are

confirmed, patients will be assigned to a cohort and given an identification number (a different number from the screening number) by the IxRS.

Patients will be assigned to one of three treatment arms based on the following stratification factors:

- Tumor grade (1 and 2 vs. 3)
- Nodal status (cytologically positive vs. radiologically or cytologically negative).
If on ultrasound examination there is evidence of suspicious axillary lymph nodes at the baseline examination, then fine-needle aspiration (FNA) or core biopsy is required to confirm nodal status.

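### Section 6.6 reports Ki67 change dose by dose and plans no between-dose estimate, although the endpoint is meant to describe a dose-activity relationship and help guide dose choice

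*Combined protocol and SAP*

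**What the plan says.** Section 6.6 contains the whole Ki67 analysis plan. Values are log-transformed after adding 0.1, and "The activity will be summarized by dose level". On intervals it says "The result of mean log changes and CI can be calculated and displayed on their original scale by back transformation". It states no confidence level, and names no contrast between doses, no trend or dose-response model, and no covariate.

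No other section fills this in. The opening of Section 6 presents all summaries by assigned dose level and cohort. Section 6.5 compares PK with historical profiles. Section 6.7 is descriptive.

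The stated purpose is comparative:

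- Section 3.3.2 describes the endpoints as "biomarkers aimed at defining dose-PD and dose-activity relationships to help guide selection of the recommended Phase II dose".
- Section 3.3.4 says "The evaluation of dose-PD and dose-activity relationships across a range of GDC-9545 doses will enable dose selection".
- Section 1.3 speaks of a "strong rationale to run a window of opportunity study to select the optimal dose of GDC-9545", with Ki67 read alongside other PD, safety and efficacy data.

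On design, Section 4.2 says "Patients will be assigned to one of three treatment arms based on the following stratification factors", namely tumor grade (1 and 2 v 3) and nodal status. The text does not say that assignment is random. Section 6.1 plans about 75 patients and states: "To better evaluate the Ki67 expression change at 30 mg, the sample size is increased to 45". The amendment rationale says that Version 4 adds 30 patients, all to the 30 mg cohort.

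**The concern.** A dose-activity relationship is a between-dose quantity, and the plan estimates none. With only three by-dose intervals to look at, the natural way to compare doses is to see whether the intervals overlap. That is a harsher criterion than a direct contrast at the same confidence level, so the display can look inconclusive when the ratio is not.

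An unadjusted ratio can be rebuilt from the by-dose results. One adjusted for baseline Ki67 and the assignment factors cannot. Adjustment is worth stating in advance because random assignment is not stated, and because 30 of the 45 patients planned at 30 mg come from a later amendment and may not be concurrent with the other cohorts.

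**Working it through.** **1. What Table 4 supplies.** The printed two-sided 80% limits follow

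change × exp(±1.2816 × s/√n), capped at 100%.

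The SD s is not printed. A single fitted value, s = 0.3235, reproduces all 12 intervals to the printed decimal. Two examples at 60%:

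- n = 45: 1.2816 × 0.3235/√45 = 0.0618, giving 60/1.0637 = 56.4 and 60 × 1.0637 = 63.8.
- n = 15: 1.2816 × 0.3235/√15 = 0.1070, giving 53.9 and 66.8.

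So Table 4 holds one-cohort intervals on the log of the percent change. Section 6.6 works on log post-treatment minus log baseline Ki67. The SD on that scale, called tau here, is not in the documents, and 0.3235 cannot stand in for it.

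**2. Overlap v contrast on Table 4's own scale.** Take 60% at n = 15 (53.9 to 66.8) and 70% at n = 45 (65.8 to 74.5). The intervals overlap. The direct ratio is 70/60 = 1.17, with SE 0.3235 × √(1/15 + 1/45) = 0.3235 × 0.2981 = 0.0964. Its 80% CI is 1.17 ×/÷ exp(1.2816 × 0.0964), or 1.03 to 1.32, which excludes 1.

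**3. The same comparison on the Section 6.6 scale.** Inputs are 15 and 45 patients (Section 6.1; 75 − 45 = 30 over two cohorts) and a common tau. The 0.1 offset is ignored. A reduction of p leaves a post/pre ratio of 1 − p, so the log ratios are ln(0.4/0.3) = 0.288, ln(0.3/0.2) = 0.405 and ln(0.2/0.1) = 0.693.

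- Separate 80% intervals are disjoint if the log ratio exceeds tau × 1.2816 × (1/√15 + 1/√45) = 0.522 tau.
- The direct 80% interval excludes 1 if the log ratio exceeds tau × 1.2934 × 0.2981 = 0.386 tau, where 1.2934 is t on 75 − 3 = 72 df.

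| Reductions compared | Disjoint if tau below | Ratio CI excludes 1 if tau below |
|---|---|---|
| 60 v 70% | 0.288/0.522 = 0.55 | 0.288/0.386 = 0.75 |
| 70 v 80% | 0.405/0.522 = 0.78 | 0.405/0.386 = 1.05 |
| 80 v 90% | 0.693/0.522 = 1.33 | 0.693/0.386 = 1.80 |

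With t quantiles for the separate intervals (1.345 on 14 df, 1.301 on 44 df) the factor is 0.541 and the middle column becomes 0.53, 0.75 and 1.28. The gap widens slightly.

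**4. Example inside the gap.** Assume tau = 0.9, with reductions of 70% at n = 15 and 80% at n = 45. The by-dose post/pre intervals are 0.3 ×/÷ exp(1.2816 × 0.9/√15) = 0.223 to 0.404 and 0.2 ×/÷ exp(1.2816 × 0.9/√45) = 0.168 to 0.238. They overlap. The direct ratio is 0.67, with 80% CI 0.67 ×/÷ exp(1.2934 × 0.9 × 0.2981) = 0.47 to 0.94.

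**5. Precision of the unadjusted ratio.** The factor is exp(1.2934 × tau × SE).

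| Contrast | SE/tau | tau 0.75 | tau 1.0 | tau 1.25 |
|---|---|---|---|---|
| 15 v 45 (all 30 mg patients) | 0.2981 | ×/÷ 1.34 | ×/÷ 1.47 | ×/÷ 1.62 |
| 15 v 15 | 0.3651 | ×/÷ 1.43 | ×/÷ 1.60 | ×/÷ 1.80 |

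The second row applies to 100 v 10 mg. It also applies to contrasts with 30 mg if only the first 45 − 30 = 15 patients at that dose count as concurrent. All tau values here are assumptions.

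**6. Cost of adjustment.** Baseline Ki67, grade and nodal status take one df each: 72 − 3 = 69. The 80% multiplier moves from 1.2934 to 1.2939.

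**The case against.** The strongest reply is that this is a Phase I study with a preliminary, descriptive activity objective. Section 6.1 disclaims power and type I error, and by-dose geometric means with intervals are a recognised way to show dose-activity. Ki67 only helps to guide dose selection, together with other data, and no passage makes a Ki67 contrast the decision rule. This stands, and it limits the point to a prespecified estimate. It does not remove the point, because estimation needs neither alpha nor power.

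It is also fair that the unadjusted ratio can be derived from the planned output, and that the gain from adjustment cannot be worked out from the documents.

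A reader might go further and take the Section 6.1 sentence "The 80% CIs show clear separation at this patient sample size" as a claim about telling cohorts of 15 and 45 apart, then set Table 4's 15 v 45 overlaps against it. The documents do not support that. The preceding sentence concerns the change at 30 mg, and the table lists one-cohort intervals under different assumed results. The natural reading is how well 45 patients distinguish possible results within that cohort.

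Finally, a pooled regression could carry bias of its own, since it mixes 30 mg patients enrolled before and after the expansion. That objection stands, and it shapes the fix.

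**Conclusion.** The point holds as an improvement to consider. The plan states a between-dose purpose and prespecifies no between-dose estimate. If interval overlap fills that role at 15 v 45, the three 10-point differences can be read as unresolved at tau values of roughly 0.55 to 0.75, 0.78 to 1.05 and 1.33 to 1.80, where the direct 80% interval excludes 1. These ranges rest on a common tau, log-normal changes, 75 evaluable patients and the planned cohort sizes. Where the true tau lies is unknown from the documents.

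Two stronger conclusions should not be drawn. The absence of a hypothesis test is not an error in a study of this kind. Nor do the figures show that the design cannot distinguish the doses: that depends on tau, and the overlap criterion understates what a contrast can show.

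**What to change.** Keep the by-dose summaries and add to Section 6.6:

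- A linear regression of log(Ki67_post + 0.1) on dose (10, 30 and 100 mg as a three-level factor), log(Ki67_pre + 0.1), tumor grade (1-2 v 3) and nodal status.
- Adjusted geometric mean ratios for 30 v 10, 100 v 30 and 100 v 10 mg with two-sided 80% intervals, labelled as estimates and not tests. The 80% level is the one used in Section 6.1.
- As a required analysis, the two contrasts involving 30 mg using only 30 mg patients enrolled concurrently with the 10 and 100 mg cohorts, shown next to the pooled result. The text should define concurrent enrollment.

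The cost is some SAP text, one extra model and 3 residual df. Baseline tumor tissue for Ki67 (Section 4.5.7) and grade and nodal status (Section 4.5.2) are already collected, so no visit or sample is added. The concurrent contrasts are less precise: about ×/÷ 1.60 against ×/÷ 1.47 pooled, unadjusted, at an assumed tau of 1.0 and with 15 concurrent patients at 30 mg. The gain from covariate adjustment may be small.
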